Safety analyses for Parts A, B, and A/B Cohort 8 will be conducted separately. Efficacy and PD analyses are applicable to Part B and Part A/B Cohort 8 only, and Part A/B Cohort 8 will be analyzed separately from other cohorts. Parts B and A/B Cohort 8 may also be pooled for analyses of safety, PD, and efficacy endpoints common to both parts. The Safety Set (defined as subjects who receive a dose of study drug) will be used for all safety analyses. The Full Analysis Set (FAS) (defined as subjects who are enrolled and dosed) will be used for all efficacy analyses in Part B and Part A/B Cohort 8. Data from all safety, efficacy, and PD endpoints will be analyzed using descriptive statistics, and presented by study visit and dose level for Parts A and B, and by study visit without separation by dose level for Part A/B Cohort 8.

Nonlinear mixed effects modeling will be applied for the PK analysis of ivacaftor for comparison of ivacaftor disposition to that of adults. The primary exposure estimates of interest are ivacaftor area under the concentration versus time curve (AUC) and minimum observed concentration (C_{\min}). Exposure of metabolites M1 and M6 will be described by descriptive statistics.

As noted above, preliminary analyses will be performed on the PK data obtained from each cohort in Part A. The PK analysis, along with safety data from Part A, will be used to appropriately confirm the dose selection for Part B (or adjust the doses if necessary) based on criteria that take into account both the C_{\min} and AUC relative to historical results in adult CF subjects. PK parameters other than C_{\min} and AUC may be considered if deemed appropriate.

For Part A/B Cohort 8, preliminary analyses of individual PK data collected on Day 4 will be used to inform subsequent dosing for that subject.

IDMC Reviews Data will be reviewed by an independent data monitoring committee (IDMC) to ensure the safety of the subjects in the study. Procedural details of the IDMC's structure and function, frequency of meetings, and data planned for review will be included in the IDMC charter, which will be finalized before the first IDMC review meeting.

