Subjects from Cohorts 2 and 3 who age out of the corresponding age cohort (Cohorts 6 or 7) at Part B Day 1 may enroll in an older age cohort in Part B with the Vertex medical monitor's permission. For example, subjects in Cohort 2 who will age out of Cohort 6 may enroll in Cohort 5; and subjects in Cohorts 3 or 4 who will age out of Cohort 7 may enroll in Cohort 6. Otherwise, subjects who will age out of the corresponding age cohort may enroll in the Extension Study.

Part B of this study includes:

- Screening Period (Day -28 to Day -1)
- Treatment Period (Day 1 to Week 24):
 - o Starting doses in Cohorts 5 and 6 of 25-mg (for subjects 5 to <7 kg on Day 1), 50-mg (for subjects 7 to <14 kg on Day 1), or 75-mg (for subjects 14 to <25 kg on Day 1) ivacaftor will be administered q12h for 24 weeks (or other suitable starting dose based on safety and PK data from Part A). At each study visit the ivacaftor dose for each subject will be reassessed based on body weight and adjusted if necessary.
 - o All subjects enrolled in Cohort 7 will receive a 25 mg dose of ivacaftor q12h until the subject reaches the age of 6 months. At each study visit after the age of 6 months, the ivacaftor dose for each subject will be reassessed based on body weight and adjusted, if necessary, as follows:
 - Subjects 5 to <7 kg will be dosed with 25 mg q12h
 - Subjects 7 to <14 kg will be dosed with 50 mg q12h
 - Subjects 14 to <25 kg will be dosed with 75 mg q12h
 - o Study visits will occur on Day 1 and Weeks 2, 4, 8, 12, 18, and 24.
 - o PK blood samples will be collected at the following time points:
 - Week 2: before the morning dose, between 2 and 4 hours and between 6 and 8 hours after the morning dose
 - Week 8: before the morning dose and 1 and 4 hours after the morning dose
 - Week 24: before the morning dose and between 2 and 4 hours after the morning dose
 - PK blood sampling at Week 24 is optional for subjects who undergo MBW (due to fasting requirements)
 - For subjects who prematurely discontinue treatment, a PK blood sample will be collected at the ETT Visit.

- o OEs will be performed at screening, Week 12, and Week 24.

[figure not shown]
All subjects who complete 24 weeks of study drug treatment will be eligible to enroll in the open-label treatment arm of an Extension Study. The Follow-up Visit will not be required for subjects who enroll in the treatment arm of this study.

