A minimum of 6 and up to approximately 10 subjects will be enrolled, with at least 4 subjects evenly distributed in the age range 1 to <3 months, to have adequate data to assess the PK and safety in this age range.

Part A/B Cohort 8 of this study includes:

- Confirmed genotype; genotype testing is expected to be initiated prior to screening and results must be available prior to Day 1

- Screening Period (Day -28 to Day -14)
 - Due to limitations in the volume of blood that should be collected from the 1- to <4-month-old age group in a 28-day span, screening should be completed at least 14 days prior to Day 1 (treatment initiation)
- Initial Treatment Period (Day 1 up to Day 15):
 - Subjects will receive an initial low dose of ivacaftor (5.7 mg q12h or 11.4 mg q12h based on their Day 1 age and weight) from Day 1 up to Day 15, as follows:

Age	Weight Range	Starting Dose
1 month	≥3 kg	5.7 mg q12h
2 months	≥3 to <5 kg	5.7 mg q12h
2 months	≥5 kg	11.4 mg q12h
3 months	≥5 kg	11.4 mg q12h

[figure not shown]
All subjects must have gestational age ≥38 weeks and weigh ≥3 kg. Subjects 3 months of age must weigh ≥5 kg on Day 1.

- Study visits will occur on Days 1, 4, and 15.
- Follow-up Telephone Call (Day 1 evening)
- PK samples will be collected before the morning dose on Day 4, and between 2 to 4 hours and between 6 to 8 hours after the Day 4 morning dose.
- The Day 4 PK data will be reviewed by the study team to determine the dose to be administered on Day 15. The subject's Day 4 PK data will be used to calculate exposure to determine a dose that is expected to bring the exposure for the subject closest to the adult median. This potential dose adjustment will be communicated in writing to the principal investigator to administer to the subject on Day 15. If all PK samples collected on Day 4 are missing or cannot be analyzed, PK samples collected on Day 15 will be used to assess whether the initial dose should be adjusted at the Week 4 Visit.
- At the Day 15 Visit, a trough PK sample will be collected before the morning dose. The ivacaftor dose will be adjusted (based on the Day 4 PK data) if necessary, to either 5.7, 11.4, 17.1, 22.8, or 25 mg, and the adjusted dose will be administered q12h starting with the evening dose on Day 15.
- Subsequent Treatment Period (Day 16 to Week 24):
 - Follow-up Telephone Call (Day 17)
 - Study visits will occur on Weeks 4, 8, 12, 18, and 24.

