 - The subject is intended to remain on the same dose from Day 15 until the subject is 4 months of age and at least 5 kg, after which the recommended age- and weight-appropriate dose(s) will be administered.
 - PK samples will be collected before the morning dose on Week 8, between 2 to 4 hours, and between 6 to 8 hours after the Week 8 morning dose.

- Additional PK samples will be collected before the morning dose on the Week 4, 12, 18, and 24 Visits to characterize the longitudinal PK profile.
- The entire treatment period of the study will be 24 weeks, after which subjects will be eligible to enroll in an Extension Study.
- Subjects who do not enroll in the Extension Study will have a Follow-up Visit within 4 weeks \pm 7 days after the last dose of study drug and a Follow-up OE within 12 weeks \pm 14 days after the last dose of study drug, (see Section 9.1.3.1).

Subjects who prematurely discontinue treatment before their last scheduled dose will be required to complete the ETT Visit, Follow-up Visit, and Follow-up OE. A PK blood sample will be collected at the ETT Visit (if the ETT Visit occurs within 3 days after the last dose of study drug).

Figure 9-2 Schematic of Part A/B Cohort 8 Study Design

OE: ophthalmologic examination

^a A Follow-up OE will occur approximately 12 weeks after last dose of study drug unless the subject enrolls in the Extension Study.

^b All subjects who complete 24 weeks of study drug treatment will be eligible to enroll in the open-label treatment arm of the Extension Study. All other subjects will be eligible to enroll in the observational arm of the Extension Study. Subjects who prematurely discontinue will have a Follow-up OE approximately 12 weeks after last dose of study drug.

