9.3 Rationale for Study Design and Study Drug Regimens

Part A of this study is designed to evaluate the safety and characterize the PK of ivacaftor in subjects <24 months of age at the time of treatment initiation. The plasma PK data obtained in Part A will be used for the confirmation (or adjustment if necessary) of planned doses for Part B, as described in Section 13.6.1. The ivacaftor doses identified for the initiation of Part A (25 mg, 50 mg, and 75 mg) are based on modeling and simulation results, as described in Section 9.3.2. Based on emerging data from Part A, these doses may be amended for ongoing cohorts or for future cohorts in Part A and Part B. Subjects may receive higher or lower doses and dosing may be amended to different weight strata as appropriate based on emerging data. If PK data from the initial 5 subjects enrolled in a cohort in Part A are insufficient to determine the appropriate dose for that age group, additional subjects may be enrolled and receive the same or a different dose. Dosing will not proceed in a particular age group in Part B until confirmation of the dose for that age group in Part A.

Part A/B Cohort 8 of this study is designed to evaluate the safety and characterize the PK of ivacaftor in subjects aged 1 to <4 months old who are ≥ 38 weeks gestation and weigh at least 3 kg at the time of treatment initiation (Day 1). Given the rapid change and uncertainty in CYP maturation in this young age range, an initial lower dose and adjustment of dosing based on a PK evaluation will help ensure appropriate exposures for these patients during the study conduct. Thus, an alternative study design will be used to study the cohort of patients aged 1 month to <4 months. At the end of study, a comprehensive evaluation using all of the data will be used to determine the optimal dose and regimen for this patient population.

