13.5.5.1 Adverse Events

TEAEs, defined as adverse events with start date or increased severity on or after the first dose of study drug through the end of participation (as applicable), will be summarized by treatment (dose level). TEAEs will hereafter be referred to as adverse events. Adverse event summary tables will include the following analyses presented by treatment (dose level):

- All adverse events
- Related (defined as possibly related or related) adverse events
- Adverse events leading to treatment discontinuation
- SAEs
- Adverse events by severity
- Adverse events by relationship

Summaries will be presented by MedDRA system organ class and preferred term using frequency counts and percentages. A subject with multiple occurrences of the same adverse event or a continuing adverse event will be counted only once, with the highest severity or relationship.

For Part A/B safety results will be summarized by visit only and not by treatment (dose level).

In addition, a table containing individual subject adverse event data for all deaths and other serious and significant adverse events will be provided.

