#### 8.4 Safety Analysis

The overall safety profile of study drug will be assessed in terms of the following safety and tolerability endpoints:

- Adverse events
- Clinical laboratory values (hematology and serum chemistry)
- OEs
- Physical examinations
- Standard 12-lead electrocardiograms
- Vital signs

Safety endpoints will be analyzed based on the Safety Set, separately for Part A and for the combined Part B and Part A/B Cohort 8. Only a descriptive analysis of safety will be performed. Summary tables will be presented by visit for each cohort, and overall. All safety data will be presented in individual subject data listings. No statistical hypothesis testing will be conducted.

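### Cohort 8 whole-period safety outputs and later visit rows pool dosing before and after the 4-month/5-kg switch, and no planned summary separates the two

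*Protocol*

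**What the plan says.** **Dosing.** Protocol 9.1 gives Cohort 8 an initial low dose up to Day 15. Any adjustment from the Day 4 PK data takes effect with the evening dose on Day 15. After that, "The subject is intended to remain on the same dose from Day 15 until the subject is 4 months of age and at least 5" (weight in kilograms). From then on the recommended age- and weight-appropriate dosing applies.

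**Presentation in the protocol.** The synopsis plans results "presented by study visit and dose level for Parts A and B", but "by study visit without separation by dose level for Part A/B Cohort 8". Sections 13.5.5.1 to 13.5.5.4 and 13.5.5.6 repeat the Cohort 8 exception for safety.

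**Presentation in the SAP.** Section 8.4 states: "Summary tables will be presented by visit for each cohort, and overall". Section 8.3 does the same for sweat chloride. The treatment-emergent period (8.1) runs from first dose to the Follow-up Visit or end of study. TEAE tables (8.4.1) count a subject once per event over that period. Sections 8.4.2 and 8.4.3 summarise one maximum on-treatment LFT and QTc per subject. Exposure (8.2.4) is last dose date minus first dose date plus 1 day.

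**Purpose.** The safety objective (Protocol 7.2.1) defines the population by age at treatment initiation. Section 9.1 adds that the cohort size is chosen "to have adequate data to assess the PK and safety in this age range". Section 9.3 says that an evaluation of all the data "will be used to determine the optimal dose and regimen for this patient population".

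**The concern.** The under-4-month dosing is what Cohort 8 adds. Protocol Appendix A ties eligibility to regions where ivacaftor is already approved from 4 months of age, so time after the switch is not the open question.

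A whole-period TEAE count, or a single maximum LFT or QTc, cannot show whether the finding arose on the initial dose, on the Day 15 dose or after the switch. The exposure summary gives one duration per infant, so it does not show how much treatment time belongs to the younger dosing. A report could then describe 24 weeks of safety in 1 to <4 month olds when much of that time was spent on the later regimen.

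**Working it through.** **The plan's own figure.** Protocol 9.3.1 and 9.3.2 say that 24 weeks gives data at least through 7 months of age. For entry at 1 month, four-week months give 1 + 168/28 = 7.0, which reproduces it. Calendar months (30.44 days) give 1 + 168/30.44 = 6.52, which does not. Both conventions are carried below where they matter.

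**Inputs.** Entry age 1 to <4 months, 6 to about 10 infants, at least 4 spread evenly over 1 to <3 months (synopsis); 168 days of treatment; visits at Days 4 and 15 and Weeks 4, 8, 12, 18 and 24. The entry-age distribution is not in the documents and is assumed. The 5 kg condition is ignored at first; it can only lengthen the time before the switch.

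**Share of treatment before 4 months** = (4 − entry age) × 30.44 / 168.

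- Entry at 1, 2 and 3 months: 91.3, 60.9 and 30.4 days, or 54%, 36% and 18%.
- Uniform over 1 to <4 months: mean 1.5 × 30.44 = 45.7 days, 27% (25% with four-week months).
- N = 6, four aged 1 to <3 and two aged 3 to <4: (4 × 2 + 2 × 0.5)/6 = 1.5 months, again 27%; in total 6 × 45.7 = 274 of 1,008 infant-days.
- N = 10, four aged 1 to <3 and six aged 3 to <4: (4 × 2 + 6 × 0.5)/10 = 1.1 months, 20% (18% with four-week months); in total 335 of 1,680 infant-days.
- All aged 1 to <3: mean 2 months, 36%.

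The initial dose alone takes 14/168 = 8%. Under uniform entry the Day 15 dose before 4 months averages (91.3 − 14)² / (2 × 91.3) = 32.7 days, 19%. These two add to 46.7 days rather than 45.7 because the initial dose runs to Day 15 even for infants who turn 4 months sooner.

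**If the switch waits for the next scheduled visit.** Under uniform entry, the time to 4 months is uniform on 0 to 91.3 days. Rounding it up to the next visit from Day 15 on gives (14×14 + 14×28 + 28×56 + 28×84 + 7.3×126)/91.3 ≈ 59.5 days, 35%. For the N = 10 mix the same rule gives 27%. With all infants entering at 1 to <3 months it gives (25.6×56 + 28×84 + 7.3×126)/60.9 ≈ 77.3 days, 46%.

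**What each visit row describes** (uniform entry, calendar months):

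| Visit | Still under 4 months | Still on pre-switch dosing on arrival, if the switch waits for a visit |
|---|---|---|
| Day 4 | 97% | all (initial dose) |
| Day 15 | 85% | all (initial dose) |
| Week 4 | 69% | 85% |
| Week 8 | 39% | 69% |
| Week 12 | 8% | 39% |
| Week 18 | 0% | 8% |
| Week 24 | 0% | 0% |

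The first column is 1 − day/91.3, with Day 4 taken as 3 days after first dose and Day 15 as 14. The second applies the same formula to the preceding visit from Week 4 on.

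**Reading the outputs against this.** Scheduled Day 4 and Day 15 assessments precede the Day 15 evening dose, so those rows already show the initial dose. Weeks 4 to 12 mix phases to a degree that depends on how the switch is made. Weeks 18 and 24 are almost wholly after it. The TEAE, maximum LFT, maximum QTc and exposure outputs have no division at all.

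**The case against.** The strongest reply is that the tables answer the stated objective. It is worded by age at initiation, Protocol 13.4 bases the analysis on the 24-week data, and treatment past 4 months is deliberate. That stands: by-cohort tables match the defined population. The gap is with the aim in 9.1 of assessing PK and safety in the age range itself.

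Doses are individualised towards one exposure target in 6 to about 10 infants, so declining to split by dose level is defensible. Individual listings are planned and will show the timing of every event. Both points stand and argue for a few phase tables rather than tables by dose. They do not supply a summary with exposure time as denominator.

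Phase is confounded with age and time on drug, and Protocol 9.3.3 notes that sweat chloride itself rises over the first 6 months. Phase tables will therefore not establish cause. This also stands.

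Four stronger readings might be inferred and are not supported:

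- *That the Cohort 8 tables as a whole mostly describe the older regimen.* The Day 4 and Day 15 rows do not, and the mix from Week 4 to Week 12 depends on entry ages and switch timing. An infant entering at 1 month spends 54% of treatment under 4 months.
- *That every infant has three different doses.* Adjustment is made only if necessary, and infants entering after about 3.54 months (4 − 14/30.44) turn 4 months before Day 15.
- *That the Week 12 and 24 eye examinations are uninformative about early dosing.* The protocol schedules a follow-up eye examination 12 weeks after the last dose for infants who stop early, so it treats lens findings as relevant after exposure ends.
- *That the regimen question cannot be answered.* Section 9.3 refers to an evaluation of all the data, and PK estimation is assigned to the CPAP, which is not among these documents.

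**Conclusion.** The point holds for the whole-period Cohort 8 outputs and the later visit rows: they pool under-4-month dosing with the later regimen, and neither document plans a summary that separates them. The pre-switch share is roughly 18–36% over the assumed entry mixes if the switch occurs at 4 months. Under uniform entry it is about 27%, or about 35% if the switch waits for a visit; waiting combined with an all-young cohort could take it to about 46%. These figures rest on assumed entry ages and ignore the 5 kg condition, which could lengthen pre-switch time and put some infants on pre-switch dosing even at Weeks 18 and 24.

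A reader might extend the point to Cohort 7, since "All subjects enrolled in Cohort 7 will receive a 25 mg dose of ivacaftor q12h until the subject reaches the age of 6 months". The documents do not support treating it as the same gap. The protocol (synopsis, 13.5.3.2.1, 13.5.5.1) plans dose-level summaries for Part B; SAP 8.3 and 8.4 leave them out. That is a protocol–SAP discrepancy. Cohort 7's uniform-entry share before 6 months is also smaller, at 30.44/168 = 18%, and infants of 5 to <7 kg stay on 25 mg after that age.

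This is an inexpensive improvement to what can be concluded, and does not invalidate the planned analysis.

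**What to change.** In SAP 8.2.4 and 8.4, add supportive descriptive tables for Cohort 8 by dosing phase at onset or sampling: (1) initial dose; (2) Day 15 dose, adjusted or not, up to the 4-month/5-kg switch; (3) after the switch. Assign phase from actual dosing dates, with a pre-stated rule for events on a changeover day. Report:

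- subjects and exposure days per phase;
- TEAEs by phase of onset, with subjects, percentages and events per exposure time;
- maximum LFT and maximum QTc per phase.

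Keep the by-visit tables. State the pre-switch exposure time wherever a conclusion is drawn about safety in 1 to <4 month olds.

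Separately, reconcile the protocol and SAP on dose-level summaries for Part B, including Cohort 7, and confirm that the CPAP reports Cohort 8 AUC and Cmin by age or phase at sampling.

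The cost is SAP wording and a few tables from dosing dates, weights and ages already collected. The downside is small cells in which phase cannot be separated from age or time on drug, so the tables must be labelled descriptive.

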3 SCHEDULE OF ASSESSMENTS

Table 3-1	Study VX15-770-124: Part A (Screening, Treatment, Early Termination of Treatment, and Follow-up Periods)
Table 3-2	Study VX15-770-124: Part B (Screening and Treatment Periods)
Table 3-3	Study VX15-770-124: Part B (Early Termination of Treatment Visit and Follow-up Period)
Table 3-4	Study VX15-770-124: Part A/B Cohort 8 (Screening, Treatment, Early Termination of Treatment, and Follow-up Periods)

Table 3-1 Study VX15-770-124: Part A (Screening, Treatment, Early Termination of Treatment, and Follow-up Periods)

Event/Assessment	Screening Period	Treatment Period					Early Termination of Treatment Visit	Follow-up Telephone Call	Follow-up Ophthalmologic Examination
	Day -28 to Day -1	Day 1	Day 2	Day 3	Day 4	Day 5	Within 5 Days After Last Dose of Study Drug	Day 14 (± 2 Days)	8 Weeks (± 14 Days) After Last Dose of Study Drug
Informed consent ^a	X								
Inclusion/exclusion criteria review	X	X							
Clinic visit	X	X			X	X	X		
Telephone contact		evening	morning					X	
Study drug count		X			X		X		
Demographics	X								
Medical history	X								
CFTR genotype ^b	X								
██████████ weight ^c	X	X				X	X		
Physical examination ^d	X	X				X	X		
Vital signs ^e	X	X				X	X		

^a Informed consent may be obtained before the Screening Visit and must be obtained before any screening assessment is performed.

^b The *CFTR* genotype results must be available before the first dose of study drug. If a genotype test has been performed previously and is documented in the subject's medical record, the subject's eligibility must be approved by the Vertex medical monitor. If a historic genotype result is not available at screening or if the historic genotype result is not approved by the Vertex medical monitor, subjects will be tested for *CFTR* genotype and the results must be reviewed before the first dose of study drug.

^c ██████████ weight must be measured with the subject in a dry diaper or dry underclothes only (see Section 12.5.1 for details). ██████████ weight measurements will be made before the morning dose on Day 1. ██████████

^d Full physical examinations will occur at the Screening Visit and the Early Termination of Treatment (ETT) Visit; abbreviated physical examinations will occur at the Day 1 and Day 5 Visits.

^e Vital signs include blood pressure (systolic and diastolic), temperature, heart rate, respiration rate, and pulse oximetry. The subject should rest for at least 5 minutes, if possible, before having vital signs measured. Day 1 vital signs measurements will be collected before the morning dose. Temperature must be obtained by the same method throughout the study.

Table 3-1 Study VX15-770-124: Part A (Screening, Treatment, Early Termination of Treatment, and Follow-up Periods)

Event/Assessment	Screening Period	Treatment Period					Early Termination of Treatment Visit	Follow-up Telephone Call	Follow-up Ophthalmologic Examination
	Day -28 to Day -1	Day 1	Day 2	Day 3	Day 4	Day 5	Within 5 Days After Last Dose of Study Drug	Day 14 (± 2 Days)	8 Weeks (± 14 Days) After Last Dose of Study Drug
12-lead ECGs ^f	X					X	X		
Ophthalmologic examination ^g	X								X
Serum chemistry and hematology ^h	X					X	X		
PK blood collection					X ⁱ	X ^j	X		
Sweat chloride test ^k	X								
Study drug administration ^l		X	X	X	X				

^f All 12-lead ECGs will be performed before the morning dose. The subject should rest for at least 5 minutes, if possible, before having the ECG performed. The ECG will be performed before any other procedures that may affect heart rate, such as blood draws.

^g The screening OE may be performed predose on Day 1. For subjects who have the Part A Follow-up OE within 6 months of enrolling in Part B, the screening OE for Part B is not required.

^h To minimize blood draws, the Screening Visit and Day 1 clinical laboratory assessments will be combined into a single blood draw taken up to 9 days before Day 1 dosing. The results must be received and reviewed before the first dose of study drug. All blood samples will be collected while subjects are in a seated or supine position.

ⁱ PK samples will be collected before the morning dose and between 2 and 4 hours and between 6 and 8 hours after dosing on Day 4.

^j A PK sample will be collected between 24 and 60 hours after Day 4 morning dose (Day 5+1 day).

^k A sweat chloride test must be performed if the sweat chloride value is not available in the subject’s medical records and the value is needed to establish eligibility. For subjects with sweat chloride values documented in their medical records and for whom it is not needed to establish eligibility, the sweat chloride test at screening is not required.

^l Study drug will be administered q12h for 3 days and the last dose of study drug in Part A will be the morning dose on Day 4. The Day 1 and Day 4 morning doses will be administered in the clinic. Doses administered from the evening dose on Day 1 through the evening dose on Day 3 will be administered q12h at home. Each dose of granules will be mixed with approximately 1 teaspoon (5 mL) of appropriate liquid or soft food (as listed in the study manual). Details

Table 3-1 Study VX15-770-124: Part A (Screening, Treatment, Early Termination of Treatment, and Follow-up Periods)

Event/Assessment	Screening Period	Treatment Period					Early Termination of Treatment Visit	Follow-up Telephone Call	Follow-up Ophthalmologic Examination
	Day -28 to Day -1	Day 1	Day 2	Day 3	Day 4	Day 5	Within 5 Days After Last Dose of Study Drug	Day 14 (± 2 Days)	8 Weeks (± 14 Days) After Last Dose of Study Drug
In-clinic observation for 4 hours after administration of the first dose of study drug		X							
Study drug dispensing		X							
Adverse events	Continuous from signing of ICF through the Follow-up Telephone Call (Day 14 ± 2 days; see Section 14.1.1.3)								Ocular adverse events only
Medications and procedures review	Continuous from 28 days before the Screening Visit through the Follow-up Telephone Call (Day 14 ± 2 days)								

CF: cystic fibrosis; *CFTR*: CF transmembrane conductance regulator gene; ECG: electrocardiogram; ETT: Early Termination of Treatment; ICF: informed consent form; OE: ophthalmologic examination; PK: pharmacokinetic; q12h: every 12 hours.

of dose preparation and dose administration will be provided in the study manual. The administration dates and times and whether doses were administered with food during the 3 days should be recorded in each subject’s dosing diary.

Table 3-2 Study VX15-770-124: Part B (Screening and Treatment Periods)

Event/Assessment	Screening Period	Treatment Period (Day 1 to Week 24)							
	Day -28 to Day -1	Day 1	Day 3	Week 2 (± 1 Day)	Week 4 (± 5 Days)	Week 8 (± 5 Days)	Week 12 (± 5 Days)	Week 18 (± 5 Days)	Week 24 ^a (± 5 Days)
Informed consent ^b	X								
Inclusion/exclusion criteria review	X	X							
Clinic visit	X	X		X	X	X	X	X	X
Telephone contact			X						
Demographics	X								
Medical history	X								
CFTR genotype ^c	X								
weight ^d	X	X		X	X	X	X	X	X
Physical examination ^e	X	X		X	X	X	X	X	X
Vital signs ^f	X	X		X	X	X	X	X	X
12-lead ECGs ^g	X				X		X		X
Ophthalmologic examinations ^h	X						X		X
Serum chemistry and hematology ⁱ	X			chemistry only	LFTs and hematology only	X	X	X	X
PK blood collection ^j				X		X			X ^k
Sweat chloride test ^l	X	X		X			X		X
Study drug administration ^q		X		X	X	X	X	X	X

^a Subjects who complete 24 weeks of study drug treatment in Part B will be eligible to enroll in the open-label treatment arm of the Extension Study. For subjects who enroll, the Week 24 visit can be the same visit as Day 1 in the treatment arm of the Extension Study, and these subjects do not need to complete

[figure not shown]
the Follow-up Visit. All other subjects must complete the ETT and/or Follow-up Visits (as applicable) and will be eligible to enroll in an observational arm of the Extension Study.

- b Informed consent may be obtained before the Screening Visit and must be obtained before any screening assessment is performed.
- c Subjects who had *CFTR* genotyping completed in Part A of the study will not require repeat testing upon entry into Part B. For all other subjects, the genotype results must be available before the first dose of study drug. If a genotype test has been performed previously and is documented in the subject's medical record, the subject's eligibility must be approved by the Vertex medical monitor. If a historic genotype result is not available at screening or if the historic genotype result is not approved by the Vertex medical monitor, subjects will be tested for *CFTR* genotype and the results must be reviewed before the first dose of study drug.
- d [REDACTED] weight must be measured with the subject in a dry diaper or dry underclothes only (see Section 12.5.1 for details). [REDACTED] weight measurements will be made before the morning dose on Day 1.
- e Full physical examinations will occur at the Screening and Week 24 Visits; abbreviated physical examinations will occur at all other study visits.
- f Vital signs include blood pressure (systolic and diastolic), temperature, heart rate, respiration rate, and pulse oximetry. The subject should rest for at least 5 minutes, if possible, before having vital signs measured. Day 1 vital signs measurements will be collected before dosing. Temperature must be obtained by the same method throughout the study.
- g All 12-lead ECGs will be performed before the morning dose. The subject should rest for at least 5 minutes, if possible, before having the ECG performed. The ECG will be performed before any other procedures that may affect heart rate, such as blood draws.
- h The screening OE may be performed predose on Day 1. If an adequate slit-lamp examination cannot be conducted at the Part B screening, subjects will not be enrolled in Part B until an adequate repeat slit-lamp examination is completed (within 4 weeks of the Screening Period) and eligibility criteria regarding the ophthalmologic findings are met. If an adequate slit-lamp examination cannot be conducted at any visit where it is required, the subject will continue to receive study drug until an adequate repeat examination is completed (within 4 weeks of the study visit); if an adequate slit-lamp examination cannot be conducted at the second examination or a lens opacity or cataract is identified, study drug dosing will be discontinued. A screening OE will not need to be conducted for subjects who have the Part A Follow-up OE within 6 months of enrolling in Part B.
- i To minimize blood draws, the Screening Visit and Day 1 clinical laboratory assessments will be combined into a single blood draw taken up to 9 days before Day 1 dosing. The results must be received and reviewed before the first dose of study drug. All blood samples will be collected while subjects are in a seated or supine position.
- j PK samples will be collected before the morning dose and between 2 and 4 hours and between 6 and 8 hours after the morning dose on Week 2. PK samples will be collected before the morning dose and 1 hour and 4 hours after the morning dose on Week 8. PK samples will be collected before the morning dose and between 2 and 4 hours after the morning dose on Week 24.
- k PK sample collection is optional at Week 24 for subjects who undergo MBW.
- l At Screening a sweat chloride test must be performed if the sweat chloride value is not available in the subject's medical records and the value is needed to establish eligibility. For subjects with sweat chloride values documented in their medical records and for whom it is not needed to establish eligibility, the sweat chloride test at screening is not required. Subjects who had a sweat chloride test during Screening for Part A will not require repeat testing during Screening for Part B. At the Day 1 Visit, the sweat chloride test must be performed before the morning dose. At the Week 2, 12, and 24 Visits, the sweat chloride test must be performed within a window of ± 2 hours relative to the morning dose of the study drug.

Table 3-2 Study VX15-770-124: Part B (Screening and Treatment Periods)

Event/Assessment	Screening Period	Treatment Period (Day 1 to Week 24)							
	Day -28 to Day -1	Day 1	Day 3	Week 2 (± 1 Day)	Week 4 (± 5 Days)	Week 8 (± 5 Days)	Week 12 (± 5 Days)	Week 18 (± 5 Days)	Week 24 ^a (± 5 Days)
In-clinic observation for 4 hours after administration of the first dose of study drug		X							
Study drug count		X		X	X	X	X	X	X
Study drug dispensing		X		X	X	X	X	X	X ^r
Adverse events	14.1.1.3								
Medications and procedures review	Continuous from 28 days before the Screening Visit through the ETT and Follow-up Visit (if required)								

CF: cystic fibrosis; *CFTR*: CF transmembrane conductance regulator gene; ECG: electrocardiogram; ICF: informed consent form; [REDACTED]
[REDACTED] LFT: liver function test; PK: pharmacokinetic; q12h: every 12 hours

^q Study drug will be administered q12h. Each dose of granules will be mixed with approximately 1 teaspoon (5 mL) of liquid appropriate liquid or soft food (as listed in the study manual). Details of dose preparation and dose administration will be provided in the study manual. The dose administration dates and times, occurrence and time of regurgitation within 1 hour after dosing, and their timing with respect to food intake, will be recorded for the 2 doses prior to each PK clinic visit in each subject’s dosing diary.

^r Study drug will only be dispensed to subjects enrolling in the open-label treatment arm of the Extension Study.

Table 3-3 Study VX15-770-124: Part B (Early Termination of Treatment Visit and Follow-up Period)

	Early Termination of Treatment Visit ^a	Follow-up Visit ^b	Follow-up Ophthalmologic Examination ^c
Event/Assessment	As Soon as Possible After the Last Dose of Study Drug	4 Weeks (± 7 Days) After the Last Dose of Study Drug	24 Weeks (± 14 Days) After the Last Dose of Study Drug
Clinic visit	X	X	
weight ^d	X	X	
Physical examination ^e	X	X	
Vital signs ^f	X	X	
12-lead ECGs ^g	X		
Serum chemistry and hematology ^h	X	X	
Ophthalmologic examination ⁱ	X		X
PK blood collection	X		
Study drug count	X		

^a Subjects who prematurely discontinue treatment before their last scheduled dose will be required to complete the ETT Visit as soon as possible after the last dose of study drug and the Follow-up Visit. All subjects who prematurely discontinue from study drug treatment in Part B will be eligible to enroll in an observational arm of the Extension Study.

^b The Follow-up Visit is not required if the subject completes the Part B treatment period and enrolls in the treatment arm of the Extension Study. For all other subjects, the Follow-up Visit is not required if the ETT Visit occurs 3 weeks or later after the last dose of study drug (ivacaftor) or in the event that the subject initiates treatment with commercially available ivacaftor within 3 weeks of the final scheduled treatment visit or ETT Visit.

^c Subjects who prematurely discontinue ivacaftor treatment in Part B and received at least 1 dose of ivacaftor treatment in Part B will have a Follow-up OE 24 weeks after the last dose of study drug. Subjects enrolling into the Extension Study within 24 weeks after the last dose of study drug are not required to have the Follow-up OE (the OE will be performed in the Extension Study instead).

^d weight must be measured with the subject in a dry diaper or dry underclothes only (see Section 12.5.1 for details).

^e Full physical examinations will be performed at the ETT Visit and Follow-up Visit.

^f Vital signs include blood pressure (systolic and diastolic), temperature, heart rate, respiration rate, and pulse oximetry. The subject should rest for at least 5 minutes, if possible, before having vital signs measured. Temperature must be obtained by the same method throughout the study.

^g The subject should rest for at least 5 minutes, if possible, before having the ECG performed. The ECG will be performed before any other procedures that may affect heart rate, such as blood draws.

^h All blood samples will be collected while subjects are in a seated or supine position.

ⁱ The OE for the ETT Visit will be conducted for all subjects who prematurely discontinue study drug dosing. If the ETT Visit occurs within 12 weeks of the subject's last OE, the OE at the ETT Visit will not be required. In addition, these subjects will be eligible to enroll in an observational arm of the Extension Study for long-term follow-up OE.

Table 3-3 Study VX15-770-124: Part B (Early Termination of Treatment Visit and Follow-up Period)

	Early Termination of Treatment Visit^a	Follow-up Visit^b	Follow-up Ophthalmologic Examination^c
Event/Assessment	As Soon as Possible After the Last Dose of Study Drug	4 Weeks (± 7 Days) After the Last Dose of Study Drug	24 Weeks (± 14 Days) After the Last Dose of Study Drug
